Appendix C Handling of Human Biological Samples

C 1 Chain of Custody

A full chain of custody is maintained for all samples throughout their life cycle.

The Investigator at each centre keeps full traceability of collected biological samples from the participants while in storage at the centre until shipment or disposal (where appropriate) and records relevant processing information related to the samples while at site.

The sample receiver keeps full traceability of the samples while in storage and during use until used or disposed of or until further shipment and keeps record of receipt of arrival and onward shipment or disposal.

AstraZeneca or delegated representatives will keep oversight of the entire life cycle through internal procedures, monitoring of study sites, auditing or process checks, and contractual requirements of external laboratory providers.

Samples retained for further use will be stored in the AstraZeneca-assigned biobanks or other sample archive facilities and will be tracked by the appropriate AstraZeneca Team during for the remainder of the sample life cycle.

C 2 Withdrawal of Informed Consent for Donated biological samples

If a participant withdraws consent to the use of donated biological samples, the samples will be disposed of/destroyed/repatriated, and the action documented. If samples are already analysed, AstraZeneca is not obliged to destroy the results of this research.

Following withdrawal of consent for biological samples, further study participation should be considered in relation to the withdrawal processes outlined in the informed consent.

The Investigator:

- Ensures participant's withdrawal of informed consent to the use of donated samples is highlighted immediately to AstraZeneca or delegate.
- Ensures that relevant human biological samples from that participant, if stored at the study site, are immediately identified, disposed of as appropriate, and the action documented.
- Ensures that the participant and AstraZeneca are informed about the sample disposal.

AstraZeneca ensures the organization(s) holding the samples is/are informed about the withdrawn consent immediately and that samples are disposed of or repatriated as appropriate, and the action documented and study site notified.

C 3 International Airline Transportation Association (IATA) 6.2 Guidance Document

LABELLING AND SHIPMENT OF BIOHAZARD SAMPLES

International Airline Transportation Association (IATA) (<https://www.iata.org/whatwedo/cargo/dgr/Pages/download.aspx>) classifies infectious substances into 3 categories: Category A, Category B or Exempt.

Category A Infectious Substances are infectious substances in a form that, when exposure to it occurs, is capable of causing permanent disability, life-threatening or fatal disease in otherwise healthy humans or animals.

Category A pathogens are eg, Ebola, Lassa fever virus. Infectious substances meeting these criteria which cause disease in humans or both in humans and animals must be assigned to UN 2814. Infectious substances which cause disease only in animals must be assigned to UN 2900.

Category B Infectious Substances are infectious substances that do not meet the criteria for inclusion in Category A. Category B pathogens are eg, hepatitis A, C, D, and E viruses. They are assigned the following UN number and proper shipping name:

- UN 3373 – Biological Substance, Category B
- are to be packed in accordance with UN 3373 and IATA 650

Exempt - Substances which do not contain infectious substances or substances which are unlikely to cause disease in humans or animals are not subject to these Regulations unless they meet the criteria for inclusion in another class.

- Clinical study samples will fall into Category B or exempt under IATA regulations.
- Clinical study samples will routinely be packed and transported at ambient temperature in IATA 650 compliant packaging (<https://www.iata.org/whatwedo/cargo/dgr/Documents/DGR-60-EN-PI650.pdf>).
- Biological samples transported in dry ice require additional dangerous goods specification for the dry ice content.

Appendix D Optional Genomics Initiative Saliva Sample

D 1 Use/Analysis of DNA

- AstraZeneca intends to collect and store DNA for genetic research to explore how genetic variations may affect clinical parameters, risk and prognosis of diseases, and the response to medications. This genetic research may lead to better understanding of diseases, better diagnosis of diseases or other improvements in health care and to the discovery of new diagnostics, treatments or medications. Therefore, where local regulations and IRB/IEC allow, a saliva sample will be collected for DNA analysis from consenting participants.
- This optional genetic research may consist of the analysis of the structure of the participant's DNA, ie, the entire genome.
- The results of genetic analyses may be reported in a separate study summary.
- The Sponsor will store the DNA samples in a secure storage space with adequate measures to protect confidentiality.
- The samples will be retained while research on AZD4573 continues but no longer than 15 years or other period as per local requirements.

D 2 Genetic Research Plan and Procedures

Selection of genetic research population

- All participants will be asked to participate in this genetic research. Participation is voluntary and if a participant declines to participate there will be no penalty or loss of benefit. The participant will not be excluded from any aspect of the main study.

Inclusion criteria

For inclusion in this genetic research, participants must fulfil all of the inclusion criteria described in the main body of the Clinical Study Protocol and provide informed consent for the Genomics Initiative sampling and analyses.

Exclusion criteria

- Exclusion from this genetic research may be for any of the exclusion criteria specified in the main study or any of the following:
 - Previous allogeneic bone marrow transplant.
 - Non-leukocyte depleted whole blood transfusion in 120 days of genetic sample collection.
 - Healthy Volunteers and paediatric patient samples will not be collected for the Genomics Initiative.

Withdrawal of consent for genetic research

- Participants may withdraw from this genetic research at any time, independent of any decision concerning participation in other aspects of the main study. Voluntary withdrawal will not prejudice further treatment. Procedures for withdrawal are outlined in Section [7.2](#) of the main Clinical Study Protocol.

Collection of samples for genetic research

- The saliva sample for this genetic research will be obtained from the patients before the first dose of IP. Although DNA is stable, early sample collection is preferred to avoid introducing bias through excluding participants who may withdraw due to an AE. If for any reason the sample is not drawn before the first dose of IP, it may be taken at any visit until the last study visit. Only one sample should be collected per participant for genetics during the study.

Coding and storage of DNA samples

- The processes adopted for the coding and storage of samples for genetic analysis are important to maintain participant confidentiality. Samples will be stored for a maximum of 15 years, from the date of last participant last visit, after which they will be destroyed. DNA is a finite resource that is used up during analyses. Samples will be stored and used until no further analyses are possible or the maximum storage time has been reached.
- An additional second code (DNA number) will be assigned to the sample either before or at the time of DNA extraction replacing the information on the sample tube. Thereafter, the sample will be identifiable only by the second, unique number. This number is used to identify the sample and corresponding data at the AstraZeneca genetics laboratories, or at the designated organization. No personal details identifying the individual will be available to any person (AstraZeneca employee or designated organizations working with the DNA).
- The link between the participant enrolment number and the second number will be maintained and stored in a secure environment, with restricted access at AstraZeneca or designated organizations. The link will be used to identify the relevant DNA samples for analysis, facilitate correlation of genotypic results with clinical data, allow regulatory audit, and permit tracing of samples for destruction in the case of withdrawal of consent.

Ethical and regulatory requirements

- The principles for ethical and regulatory requirements for the study, including this genetics research component, are outlined in [Appendix A](#).

Informed consent

- The genetic component of this study is optional, and the participant may participate in other components of the main study without participating in this genetic component. To participate in the genetic component of the study the participant must sign and date both the consent form for the main study and the addendum for the Genomics Initiative component of the study. Copies of both signed and dated consent forms must be given to the participant and the original filed at the study centre. The principal Investigator(s) is responsible for ensuring that consent is given freely and that the participant understands that they may freely withdrawal from the genetic aspect of the study at any time.

Participant data protection

- AstraZeneca will not provide individual genotype results to participants, any insurance company, any employer, their family members, or general physician unless required to do so by law.
- Extra precautions are taken to preserve confidentiality and prevent genetic data being linked to the identity of the participant. In exceptional circumstances, however, certain individuals might see both the genetic data and the personal identifiers of a participant. For example, in the case of a medical emergency, an AstraZeneca Physician or an Investigator might know a participant's identity and also have access to his or her genetic data. Regulatory authorities may require access to the relevant files, though the participant's medical information and the genetic files would remain physically separate.

Data management

- Any genetic data generated in this study will be stored at a secure system at AstraZeneca and/or designated organizations to analyse the samples.
- AstraZeneca and its designated organizations may share summary results (such as genetic differences from groups of individuals with a disease) from this genetic research with other researchers, such as hospitals, academic organizations or health insurance companies. This can be done by placing the results in scientific databases, where they can be combined with the results of similar studies to learn even more about health and disease. The researchers can only use this information for health-

related research purposes. Researchers may see summary results, but they will not be able to see individual participant data or any personal identifiers.

- Some or all of the clinical datasets from the main study may be merged with the genetic data in a suitable secure environment separate from the clinical database.
- The results of the Genomics Initiative research will be reported separately and will not form part of the Clinical Study Report.

Appendix E Actions Required in Cases of Increases in Liver Biochemistry and Evaluation of Hy's Law

E 1 Introduction

This appendix describes the process to be followed in order to identify and appropriately report Potential Hy's Law (PHL) cases and Hy's Law (HL) cases. It is not intended to be a comprehensive guide to the management of elevated liver biochemistries.

Specific guidance on managing liver anomalies can be found in the Dose Modification section of each module in the Clinical Study Protocol.

During the course of the study the Investigator will remain vigilant for increases in liver biochemistry. The Investigator is responsible for determining whether a participant meets PHL criteria at any point during the study.

All sources of laboratory data are appropriate for the determination of PHL and HL events; this includes samples taken at scheduled study visits and other visits including central and all local laboratory evaluations even if collected outside of the study visits; for example, PHL criteria could be met by an elevated ALT from a central laboratory **and/or** elevated total bilirubin (TBL) from a local laboratory.

The Investigator will also review Adverse Event data (for example, for AEs that may indicate elevations in liver biochemistry) for possible PHL events.

The Investigator will participate, together with the Medical Monitor, in review and assessment of PHL events to agree whether HL criteria are met. HL criteria are met if there is no alternative explanation for the elevations in liver biochemistry.

The Investigator is responsible for recording data pertaining to PHL/HL cases and for reporting AEs and SAEs according to the outcome of the review and assessment in line with standard safety reporting processes.

E 2 Definitions

Potential Hy's Law (PHL)

Aspartate Aminotransferase (AST) or Alanine Aminotransferase (ALT) $\geq 3 \times$ Upper Limit of Normal (ULN) **together with** TBL $\geq 2 \times$ ULN at any point during the study following the start of study medication irrespective of an increase in Alkaline Phosphatase (ALP).

Hy's Law (HL)

AST or ALT $\geq 3 \times$ ULN **together with** TBL $\geq 2 \times$ ULN, where no other reason, other than the IMP, can be found to explain the combination of increases, eg, elevated ALP indicating cholestasis, viral hepatitis, another drug.

For PHL and HL the elevation in transaminases must precede or be coincident with (ie, on the same day) the elevation in TBL, but there is no specified timeframe within which the elevations in transaminases and TBL must occur.

E 3 Identification of Potential Hy's Law Cases

In order to identify cases of PHL it is important to perform a comprehensive review of laboratory data for any participant who meets any of the following identification criteria in isolation or in combination:

- ALT $\geq 3 \times$ ULN
- AST $\geq 3 \times$ ULN
- TBL $\geq 2 \times$ ULN

Local laboratories being used:

The Investigator will without delay review each new laboratory report and if the identification criteria are met will:

- Notify the AstraZeneca representative (Medical Monitor)
- Determine whether the participant meets PHL criteria (see Section [E 1 Definitions](#) within this appendix for definition) by reviewing laboratory reports from all previous visits
- Promptly enter the laboratory data into the laboratory eCRF

E 4 Follow-up

E 4.1 Potential Hy's Law Criteria Not Met

If the participant does not meet PHL criteria the Investigator will:

- Inform the AstraZeneca representative that the participant has not met PHL criteria.
- Perform follow-up on subsequent laboratory results according to the guidance provided in the Clinical Study Protocol.

E 4.2 Potential Hy's Law Criteria Met

If the participant does meet PHL criteria the Investigator will:

- Determine whether PHL criteria were met at any study visit prior to starting study treatment (see Section [E 6](#))
- Notify the AstraZeneca representative who will then inform the central Study Team
- Within 1 day of PHL criteria being met, the Investigator will report the case as an SAE; serious criteria ‘Important Medical Event’ and causality assessment ‘yes/related’ according to CSP process for SAE reporting.
 - Events that meet PHL criteria will be reported as an SAE with the reported term “Potential Hy’s Law” ONLY if:
 - * The ALT and bilirubin elevations did not improve by Day 3 from Start of Infusion (SOI) or resolve back to baseline by Day 5, and/or
 - * INR $\geq 1.5 \times$ ULN (or an absolute increase of $0.3 \times$ baseline if elevated at baseline) of any duration at the time of ALT elevation, and/or
 - * Was accompanied by clinical symptoms of liver impairment including fatigue, nausea, vomiting, abdominal pain, and/or
 - * Required hospitalization for monitoring or treatment, or was considered clinically relevant by the investigator
 - Events that meet PHL criteria but do not fulfil the above characteristics will be reported as a SAE with the investigator-reporter term (such as AST/ALT elevations, bilirubin elevation, transaminase elevation, etc.) per the investigator’s discretion.
- Of note, all cases that meet the standard PHL criteria must be reported. The above characteristics are only to guide which reported term to use for these cases.
- The Study Physician contacts the Investigator, to provide guidance, discuss and agree an approach for the study participants’ follow-up (including any further laboratory testing) and the continuous review of data
- Subsequent to this contact the Investigator will:
 - Monitor the participant until liver biochemistry parameters and appropriate clinical symptoms and signs return to normal or baseline levels, or as long as medically indicated. Completes follow-up SAE Form as required.
 - Investigate the aetiology of the event and perform diagnostic investigations as discussed with the Study Physician.
 - Complete Liver/PHL eCRF modules/forms as information becomes available.

E 5 Review and Assessment of Potential Hy's Law Cases

The instructions in this section should be followed for all cases where PHL criteria are met.

As soon as possible after the biochemistry abnormality was initially detected, the Study Physician contacts the Investigator in order to review available data and agree on whether there is an alternative explanation for meeting PHL criteria, to ensure timely analysis and SUSAR reporting to Health Authorities in an expedited manner. The AstraZeneca Global Clinical Lead or equivalent and Global Safety Physician will also be involved in this review together with other subject matter experts as appropriate.

According to the outcome of the review and assessment, the Investigator will follow the instructions below.

Where there is an agreed alternative explanation for the ALT or AST and TBL elevations, a determination of whether the alternative explanation is an AE will be made and subsequently whether the AE meets the criteria for a SAE:

- If the alternative explanation is **not** an AE, record the alternative explanation on the appropriate eCRF.
- If the alternative explanation is an AE/SAE: update the previously submitted PHL SAE and AE eCRFs accordingly with the new information (reassessing event term; causality and seriousness criteria) following the AstraZeneca standard processes.

If it is agreed that there is **no** alternative explanation for the ALT or AST and TBL elevations:

- Send updated SAE (report term 'Hy's Law') according to AstraZeneca standard processes.
 - The 'Medically Important' serious criterion should be used if no other serious criteria apply.
 - As there is no alternative explanation for the HL case, a causality assessment of 'related' should be assigned.

If, there is an unavoidable delay, of over 15 calendar days in obtaining the information necessary to assess whether or not the case meets the criteria for HL, then it is assumed that there is no alternative explanation until such time as an informed decision can be made:

- Continue follow-up and review according to agreed plan. Once the necessary supplementary information is obtained, repeat the review and assessment to determine whether HL criteria are still met. Update the previously submitted PHL SAE report following CSP process for SAE reporting, according to the outcome of the review and amending the reported term if an alternative explanation for the liver biochemistry elevations is determined.

E 6 Actions Required When Potential Hy's Law Criteria are Met Before and After Starting Study Treatment

This section is applicable to participants with liver metastases who meet PHL criteria on study treatment, having previously met PHL criteria at a study visit prior to starting study treatment.

At the first on-study treatment occurrence of PHL criteria being met the Investigator will determine if there has been a **significant change** in the participants' condition[#] compared with the last visit where PHL criteria were met[#]

- If there is no significant change no action is required
- If there is a significant change, notify the AstraZeneca representative, who will inform the central Study Team, then follow the subsequent process described in Section [E 4.2](#)

E 7 Actions Required for Repeat Episodes of Potential Hy's Law

This section is applicable when a participant meets PHL criteria on study treatment and has already met PHL criteria at a previous on study treatment visit (Section [E 6](#)).

The requirement to conduct follow-up, review and assessment of a repeat occurrence(s) of PHL is based on the nature of the alternative cause identified for the previous occurrence.

The Investigator should determine the cause for the previous occurrence of PHL criteria being met and answer the following question:

Was the alternative cause for the previous occurrence of PHL criteria being met found to be the disease under study eg, chronic or progressing malignant disease, severe infection or liver disease?

If **No**: follow the process described in Section [E 4.2](#) for reporting PHL as an SAE

If Yes: Determine if there has been a significant change in the participant's condition[#] compared with when PHL criteria were previously met

- If there is no significant change no action is required
- If there is a significant change follow the process described in Section [E 4.2](#) for reporting PHL as an SAE

E 8 Laboratory Tests

Proposed laboratory assessments to be performed as judged by the investigator	
Additional standard chemistry and coagulation tests	GGT LDH Prothrombin time INR
Viral hepatitis	IgM anti-HAV HBsAg IgM and IgG anti-HBc HBV DNQ ^a IgG anti-HCV HCV RNA ^b IgM anti-HEV HEV RNA
Other viral infections	IgM & IgG anti-CMV IgM & IgG anti-HSV IgM & IgG anti-EBV
Alcoholic hepatitis	Carbohydrate deficient transferrin (CD-transferrin) ^c
Autoimmune hepatitis	Antinuclear antibody (ANA) Anti-Liver/Kidney Microsomal Ab (Anti-LKM) Anti-Smooth Muscle Ab (ASMA)
Metabolic diseases	alpha-1-antitrypsin Ceruloplasmin Iron Ferritin Transferrin ^c Transferrin saturation

^a HBV DNA is only recommended when IgG anti-HBc is positive

^b HCV RNA is only recommended when IgG anti-HCV is positive or inconclusive

^c CD-transferrin and Transferrin are not available in China. Study teams should amend this list accordingly

E 9 References

Aithal et al, 2011

Aithal GP, Watkins PB, Andrade RJ, Larrey M, Molokhia M, Takikawa H, et al. Case definition and phenotype standardization in drug-induced liver injury. Clin Pharmacol Ther. 89(6):806-15.

FDA Guidance for Industry, July 2009

FDA Guidance for Industry (July 2009) Drug-induced liver injury: premarketing clinical evaluation. <https://www.fda.gov/regulatory-information/search-fda-guidance-documents/drug-induced-liver-injury-premarketing-clinical-evaluation>. Accessed 06 April 2021.

Appendix F Cairo-Bishop Tumour Lysis Syndrome Definition and Grading Criteria (Howard Modification)

Laboratory tumour lysis syndrome (TLS) is defined as a level above or below normal, as defined below, for any 2 or more serum values of uric acid, potassium, phosphate, and calcium within 3 day before or 7 day after the initiation of anti-cancer therapy. This assessment assumes that a participant has or will receive adequate hydration and a hypouricemic agent(s).

Cairo-Bishop Definition of Laboratory Tumour Lysis Syndrome (Howard Modification)

Element	Value
Uric Acid	$\geq 476 \mu\text{mol/L}$ (8 mg/dL)
Potassium	$\geq 6.0 \text{ mmol/L}$ (6 mg/L)
Inorganic phosphorus	$\geq 1.45 \text{ mmol/L}$ (4.5 mg/dL)
Calcium	$\leq 1.75 \text{ mmol/L}$ (7.0 mg/dL)

Howard et al 2011

Cairo-Bishop Definition of Clinical Tumour Lysis Syndrome

Clinical tumour lysis syndrome (TLS) assumes the laboratory evidence of metabolic changes and significant clinical toxicity that requires clinical intervention. Clinical TLS is defined as the presence of laboratory TLS and any 1 or more of the below-mentioned criteria. Maximal clinical TLS manifestation (renal, cardiac, neuro) defines the grade.

- 1 Creatinine $\geq 1.5 \times \text{ULN}$ (age > 12 years or age adjusted)
- 2 Cardiac arrhythmia/sudden death
- 3 Seizure

Cairo-Bishop Clinical Tumour Lysis Syndrome Grading Criteria

Complication	Grade					
	0	1	2	3	4	5
Creatinine*,†	$< 1.5 \times \text{ULN}$	$1.5 \times \text{ULN}$	$> 1.5 - 3.0 \times \text{ULN}$	$> 3.0 - 6.0 \times \text{ULN}$	$> 6.0 \times \text{ULN}$	Death

Complication	Grade					
	0	1	2	3	4	5
Cardiac Arrhythmia*	None	Intervention not indicated	Nonurgent medical intervention indicated	Symptomatic and incompletely controlled medically or controlled with device (eg, defibrillator)	Life-threatening (eg, arrhythmia associated with CHF, hypotension, syncope, shock)	Death
Seizure*	None	None	One brief, generalised seizure; seizure(s) well controlled by anticonvulsants or infrequent focal motor seizures not interfering with ADL	Seizure in which consciousness is altered; poorly controlled seizure disorder; with breakthrough generalised seizures despite medical intervention	Seizure of any kind which are prolonged, repetitive or difficult to control (eg, status epilepticus, intractable epilepsy)	Death

ADL = activities of daily living; CHF = congestive heart failure; CTLS = clinical tumour lysis syndrome; LTLS = laboratory tumour lysis syndrome; ULN = upper limit of normal

Clinical tumour lysis syndrome (CTLS) requires one or more clinical manifestations along with criteria for LTLS. Maximal CTLS manifestation (renal, cardiac, neuro) defines the grade.

*Not directly or probably attributable to therapeutic agent (eg, rise in creatinine after amphotericin administration).

†If no institutional ULN is specified, age/sex ULN creatinine may be defined as 105.6 µmol/L for female participants ≥ 16 years of age and 114.4 µmol/L for male participants ≥ 16 years of age.

Modified from [Cairo and Bishop 2004](#).

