If bilirubin fails to resolve within 96 hours (-2/+12 hours) or transaminases fail to resolve within 7 days, or if the event is associated with significant clotting abnormality or clinical symptoms of liver disease, study treatment must be permanently discontinued (the participant remains on study for the 30-day SFU and long-term follow-up [LTFU] visits), and the event must be immediately communicated to AstraZeneca.

For guidance on treating liver toxicity, please refer to [Table 32](#) of this protocol.

During the course of the study the Investigator will remain vigilant for increases in liver biochemistry. The Investigator is responsible for determining whether a participant meets PHL criteria at any point during the study.

Please refer to [Appendix E](#) for the process to be followed to identify and appropriately report events of PHL. It is not intended to be a comprehensive guide to the management of elevated liver biochemistries.

The Investigator will participate, together with the Medical Monitor, in review and assessment of PHL events to agree whether HL criteria are met. HL criteria are met if there is no alternative explanation for the elevations in liver biochemistry.

The Investigator is responsible for recording data pertaining to PHL/HL cases and for reporting AEs and SAEs according to the outcome of the review and assessment in line with standard safety reporting processes.

Regarding the hepatic toxicity events encountered to date with AZD4573, it has been observed that while the biochemical changes of increased transaminase with concomitant elevation in

bilirubin seen in some participants could be classified as HL by its strict definition, they do not follow a pattern that is consistent with true HL predictive of hepatic injury, and are therefore 'PHL' cases. The events are rapidly resolved and to date have not led to any clinical sequelae or lasting hepatic injury. Repeated dosing with AZD4573 following these events has demonstrated that there is no consistent pattern of recurrence and no consistent increase in severity of the events if they do recur.

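### Counts of Potential Hy's Law and Hy's Law by reported term are unreliable, because the Appendix E term rule omits AST, needs results that arrive after the report is due, and conflicts with E 5 and Section 26.1.10.9

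*Protocol*

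**What the plan says.** **Definitions (Appendix E 2).** PHL requires a transaminase of at least 3 × ULN together with total bilirubin (TBL) of at least 2 × ULN. Either enzyme counts: the definition opens "Aspartate Aminotransferase (AST) or Alanine Aminotransferase (ALT". Hy's Law (HL) is the same biochemistry "where no other reason, other than the IMP, can be found to explain the combination of increases".

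**Deadline (E 4.2).** "Within 1 day of PHL criteria being met, the Investigator will report the case as an SAE".

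**Term rule (E 4.2).** The term Potential Hy's Law is allowed only if one or more of these hold:
- an unfavourable course: "The ALT and bilirubin elevations did not improve by Day 3 from Start of Infusion (SOI) or resolve back to baseline by Day 5";
- a raised INR "of any duration at the time of ALT elevation";
- clinical symptoms such as fatigue, nausea, vomiting or abdominal pain;
- hospitalisation, or the investigator's judgement that the event is clinically relevant.

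A case with none of these "will be reported as a SAE with the investigator-reporter term", at the investigator's discretion. E 4.2 adds that every case meeting standard PHL criteria must be reported and that the listed features guide the term only.

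**Review (E 5).** "The instructions in this section should be followed for all cases where PHL criteria are met". If the review finds no alternative explanation, an updated SAE goes out under the term Hy's Law.

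**Module 2 safety text (26.1.10.9).** The AZD4573 liver events seen so far "could be classified as HL by its strict definition, they do not follow a pattern that is consistent with true HL predictive" of liver injury, and the text therefore calls them PHL cases. Section 26.1.10.3 repeats this.

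**The concern.** Transaminase elevation with raised bilirubin is an important identified risk of AZD4573, and the combination risk table in Section 20.3.1 describes self-limiting events meeting PHL criteria as very common with monotherapy. Adverse events, including SAEs, are a Module 2 primary endpoint (Table 26). Sections 18.4.4 and 27.4.4 summarise them by MedDRA system organ class and preferred term, so the reported term decides the row in which a case is counted. Section 27.5 has the Safety Review Committee compare MCL safety with the known DLBCL profile.

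If similar events can carry different terms depending on which enzyme rose, when the term was chosen or which section was followed, the PHL and HL rows measure reporting practice as well as liver toxicity.

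**Working it through.** The plan states no figure on this point to reproduce. The check is a comparison of texts plus clock arithmetic.

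**1. Which enzyme.** Take an AST-driven case: AST at least 3 × ULN, TBL at least 2 × ULN, ALT not elevated, both abnormalities persisting.
- E 2: PHL criteria are met.
- E 4.2, course: not met, because there is no ALT elevation that could fail to improve or resolve.
- E 4.2, INR: tied to an ALT elevation that does not exist, so the case has no defined path through it.
- E 4.2, symptoms, hospitalisation or clinical relevance: not tied to ALT, so still available.
- Table 32: TBL not back to baseline within 96 h, and/or AST or ALT not back within 7 days, means discontinuation of both drugs.

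The dosing table thus recognises persistent AST-driven cases, while the E 4.2 persistence bullet does not.

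**2. Timing.** Inputs from Section 26.1.7: chemistry at 24 h after the start of infusion (Cycles 1 to 3); repeat liver tests at 48 h and 96 h, each −2/+12 h. From E 4.2: report within 1 day. Assumption: the infusion day is Day 1, so Day 3 is about 48 h and Day 5 about 96 h, matching the repeat tests.
- Deadline for an event found at 24 h: 24 + 24 = 48 h.
- Day 3 window: 48 − 2 = 46 h to 48 + 12 = 60 h, which is 2 h before to 12 h after the deadline.
- Day 5 window: 96 − 2 = 94 h to 96 + 12 = 108 h. Against the deadline: 94 − 48 = 46 h to 108 − 48 = 60 h late.
- For the Day 5 result to be in hand by the deadline, PHL must first be met no earlier than 94 − 24 = 70 h to 108 − 24 = 84 h.

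If Day 3 and Day 5 instead mean 72 h and 120 h after the start of infusion, the gaps are 72 − 48 = 24 h and 120 − 48 = 72 h. For an event found at 24 h, the course criterion cannot be fully settled by the deadline under either reading.

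**3. One event, three labels.** Take a case meeting PHL criteria at 24 h, back to baseline by 96 h, with no symptoms, raised INR or hospitalisation, not judged clinically relevant, and no cause other than AZD4573.
- E 4.2: investigator's own term; Potential Hy's Law is not allowed.
- E 5: Hy's Law, because there is no alternative explanation. Rapid resolution is not an alternative cause under E 2.
- 26.1.10.9: PHL and not true HL. The same section also says HL criteria are met when there is no alternative explanation, so it is at odds with itself.

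**4. INR limit when baseline is raised.** E 4.2 uses an absolute increase of 0.3 × baseline; Table 32 and Section 24.9.1 use 1.5 × baseline. For an assumed baseline INR of 1.4: 1.4 + 0.3 × 1.4 = 1.82, against 1.5 × 1.4 = 2.10.

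**The case against.** The strongest reply is that nothing is lost. E 2 fixes one biochemical definition, every case meeting it must be reported as an SAE, the values go into the laboratory eCRF and Liver/PHL forms are completed. A reader might infer that PHL and HL counts cannot be interpreted at all. The documents do not support that, because a count from the E 2 criteria can be recovered. What fails is the count by reported term.

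Second, E 4.2 sets a first term and E 5 is a later joint review by the investigator and sponsor physicians that updates it. A reader might infer that the HL count could be anything from none to all of the affected cases, depending on the paragraph a site follows. That would require sites to skip a review that is mandatory for every case. The sequence does not remove the conflict, however: E 5 changes the term on causality, and 26.1.10.9 tells the same sites that these events are not true HL.

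Third, E 4.2 mentions a follow-up SAE form as required, so an early report and a later correction are possible. That is fair, but no sentence makes the first term provisional or says to change it on the Day 3 or Day 5 result.

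Fourth, a reader might infer that persistent AST-driven cases vanish from the PHL term. They need not: the symptom, hospitalisation and clinical-relevance criteria are open to them, and a case that forces discontinuation is likely to be judged clinically relevant.

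Fifth, the INR limits serve different purposes, a reporting term in E 4.2 and dosing in Table 32 and 24.9.1. The difference may be deliberate and is not by itself an error.

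Finally, the SAP is not shown and may already derive PHL from laboratory data, so the absence of such a table from 27.4.4 is not itself a fault. The faults in E 4.2, E 5 and 26.1.10.9 stand in the protocol whatever the SAP says.

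**Conclusion.** The point holds as a defect of the reported terms. E 4.2 omits AST from two of its criteria, makes the term depend on information that comes about 46 to 60 h after the deadline for an event found at 24 h, and disagrees with E 5 and 26.1.10.9 on the final label of a rapidly resolving event with no alternative cause. The Potential Hy's Law row will under-count cases meeting PHL criteria, and the reading of the Hy's Law row depends on how E 5 and 26.1.10.9 are squared.

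The number of cases affected is not known, because the protocol gives no rate. Purely for scale, an assumed 10% to 30% of the approximately 12 participants in Section 27.2 gives 12 × 0.10 = 1.2 to 12 × 0.30 = 3.6 with an event meeting PHL criteria. The number with conflicting labels may be smaller. Section 26.1.10.3 reports nausea and vomiting in about half of those dosed, and such symptoms accompanying the event would qualify it for the PHL term. Section 18.5 also records a decision to halt enrolment permanently.

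The timing result rests on Day 1 being the infusion day and on detection at the scheduled 24 h sample.

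**What to change.** 1. In E 4.2, word the course and INR bullets so that they match the AST-or-ALT definition in E 2.
2. State that the term on the 1-day SAE report is provisional and is finalised in a follow-up SAE report once the Day 5 result is known. Say what Day 3 and Day 5 mean in hours.
3. Reconcile E 4.2, E 5 and 26.1.10.9 (with the repeated text in 26.1.10.3) so that one final term applies to an event that met PHL criteria, resolved rapidly and has no alternative cause. Which term that is remains the sponsor's decision.
4. Base the PHL count on the E 2 laboratory criteria, including its rule that the transaminase rise precedes or coincides with the TBL rise, and not on the reported term. Splitting it by resolution within 96 h would help the reader. If the SAP already does this, a cross-reference is enough.
5. Reconcile the raised-baseline INR limits in E 4.2 and in Table 32 and 24.9.1, or state that the difference is intended. This review does not choose a limit.

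The cost is amendment wording and one laboratory-derived table. No visit or sample is added. The laboratory-based PHL count may be higher than the count by term.
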